Study Protocol Document

Community Collaboration to Advance Racial/Ethnic Equity in CRC Screening

NCT Number: NCT05714644

10/02/2025

Description of Study:

This is a pragmatic, multilevel randomized clinical trial with randomization at the level of the Community Health Center (CHC) to compare two population outreach approaches to increase colorectal cancer (CRC) screening uptake among diverse and multilingual patients: (1) mailed FIT outreach with text reminders, and (2) mailed FIT-DNA with the standard manufacturer's patient support program. Participants with an abnormal FIT or FIT-DNA result are offered telephone navigation to encourage colonoscopy completion. We hypothesized that (1) CRC screening participation would increase in both study arms; and (2) that the FIT-DNA arm would have higher participation given the centralized patient support program and appeal of the 3-year screening interval.

Objective:

The objective of this study was to compare two mailed population outreach approaches to increase colorectal cancer screening uptake among screening-eligible adults in community health centers. The primary outcome was CRC screening test completion rate using any screening modality (FIT, FIT-DNA, colonoscopy) at 90 days after the screening test was mailed in each study arm. Secondary outcomes included the screening completion rate at 180 days and the rate of completion of follow-up colonoscopy within 180 days (6 months) of an abnormal stool test result among participants with an abnormal screening test result.

Design:

This was a cluster randomized controlled trial conducted in 8 CHCs and an additional site in a non-randomized parallel protocol.

Methods:

Individuals in the designated CHCs were eligible if they were: (1) age 45 to 75; (2) overdue for CRC screening (no FIT or fecal occult blood test [FOBT] in the past year, FIT-DNA in the prior 3 years, or colonoscopy in the past 10 years); (3) under the active care of a primary

care provider at the site; and (4) spoke English or Spanish. Individuals were excluded who did not have a physical mailing address or phone number listed in the electronic health record (EHR), had prior documentation of CRC, Crohn's Disease, or ulcerative colitis, or had prior abnormal colonoscopy result (i.e., prior adenoma, sessile serrated lesion).

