Randomization was limited to the 8 CHCs in Boston and LA. We used CHC-level cluster randomization to minimize the chance of contamination within practices. Within each region, we considered the permutations of assigning the four CHCs into two arms. We chose the permutation with the closest patient volume, racial distribution, and baseline CRC screening rate, then randomly assigned the groups to one of the two study arms. Neither patients nor sites were blinded to the allocation.

In both arms, participants received an invitation letter that provided elements of informed consent via mail with the opportunity to opt out of the study. Intervention components were delivered in English or Spanish, based on patient preference as recorded in the EHR.

FIT-DNA arm. Participants were mailed a FIT-DNA kit from Exact Sciences with instructions on how to complete and return the kit to their laboratory using a standard pre-paid mailer. Participants in this arm received the standard patient support program delivered by Exact Sciences, including telephone calls, text messages, and emails in the users' preferred language to encourage completion of the kit.

FIT arm. Patients received a primer text message to inform them that a FIT kit would soon arrive at their home address. Participants then received the FIT kit in a separate mailing with a graphic instruction sheet. Two additional reminder text messages were sent. In each CHC, we used the FIT kit brand already in routine use (Boston: Polymedco; LA and SD: Hemosure iFOB test).

Navigation for patients with abnormal FIT or FIT-DNA. Participants in Boston and LA with an abnormal FIT or FIT-DNA result were offered standardized phone navigation by non-clinical team members proficient in English or Spanish, to address barriers to colonoscopy and encourage completion. In SD, patients with an abnormal FIT or FIT-DNA result received usual care follow-up, which included non-standardized outreach from clinical staff.

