Statistical Analysis Plan

Community Collaboration to Advance Racial/Ethnic Equity in CRC Screening

NCT Number: NCT05714644

8/20/2025

All sociodemographic, clinical, and outcome data were obtained from electronic health record EHR. Patient characteristics will be presented as means with standard deviations (continuous) or frequencies and proportions (categorical). For the RCT, the primary intent-to-treat analysis included all study participants who did not opt-out from the Boston and LA CHCs. A secondary analysis used a propensity score matched sample to ensure balance between the two groups on age, gender, race/ethnicity and insurance status. We also conducted a sensitivity analysis excluding participants who might have completed screening before receiving the mailed screening kit, defined as within 7 days after the kit was sent. A final analysis included participants from SD in the FIT-DNA arm.

We compared the proportions of eligible individuals who participated in screening within 90 days or 180 days between study arms using logistic regression models with the generalized estimating equations to account for the correlated nature of data within CHCs, adjusting for age and race/ethnicity, which were unbalanced between the two arms. We compared time to screening participation between the two arms using a log-rank test. We also explored the heterogeneity of treatment effect by conducting subgroup analyses for pre-specified subgroups of interest (region, race/ethnicity, age, and language) and added insurance subgroups as a post hoc comparison. Among participants who returned stool tests within 180 days, we compared the distribution of test results between study arms using Fisher's exact tests. Among those with an abnormal stool test result, we compared the rate of colonoscopy completion within 180 days by arm and region using Fisher's exact tests and compared time to colonoscopy completion between the two arms using a log-rank test. All analyses were conducted using SAS version 9.4 (Cary, NC).

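### Four arm comparisons use log-rank or Fisher's exact tests that ignore randomization by health center, so their 5% level is not assured; time to screening is the most exposed

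*SAP*

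**What the plan says.** The Protocol (Methods) makes the CHC the unit of allocation: "We used CHC-level cluster randomization to minimize the chance of contamination within practices". Eight CHCs were randomized, four in each of two regions. Allocation was restricted within region: "We chose the permutation with the closest patient volume, racial distribution, and baseline CRC screening rate", after which the two groups were assigned to arms at random.

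The SAP (second paragraph) analyzes the 90- and 180-day screening proportions by "logistic regression models with the generalized estimating equations to account for the correlated nature of data within CHCs". The other arm comparisons in that paragraph are stated as follows:

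- Time to screening: "We compared time to screening participation between the two arms using a log-rank test".
- Stool-test results, among those who returned a test: "we compared the distribution of test results between study arms using Fisher's exact tests".
- Colonoscopy completion, among those with an abnormal result: "we compared the rate of colonoscopy completion within 180 days by arm and region using Fisher's exact tests".
- Time to colonoscopy, in the same patients: "compared time to colonoscopy completion between the two arms using a log-rank test".

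No robust variance, frailty term, stratification or CHC-level summary is stated for any of these four. Of the four, only colonoscopy completion is an outcome in the Protocol (Objective), which lists as secondary "the rate of completion of follow-up colonoscopy within 180 days (6 months) of an abnormal stool test result".

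**The concern.** The SAP accepts that patients in the same CHC are correlated, then uses that fact for some arm comparisons and not for others. When CHCs are randomized, variation between CHCs is part of the error of every arm contrast. Ordinary log-rank and Fisher's exact tests count only variation between patients. Their p-values are therefore too small whenever residual between-CHC variation is present and the number analyzed per CHC is not very small.

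Two consequences matter. First, time to screening uses the whole cohort and so has the largest clusters. It could show a significant arm difference beside non-significant clustered results at 90 and 180 days, and be read as evidence that one outreach approach works faster. Second, a named secondary outcome is tested without an assured error rate, and a reader cannot judge from the documents whether the distortion is trivial or large.

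**Working it through.** The documents give no sample size, ICC, event count or significance level, so there is no planned figure to reproduce.

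**Inputs from the documents:** 8 CHCs, four per region, allocated within region (Protocol, Methods); 180-day follow-up (Protocol, Objective); the tests listed above (SAP, second paragraph).

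**Assumptions:** two CHCs per arm in each region, so 4 v 4; two-sided 5%; equal CHC sizes *m*; the ICCs and event rates shown below.

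**Step 1. Formula.** Design effect DE = 1 + (m − 1) × ICC. The true level of a nominal 5% test that ignores clustering is about 2 × [1 − Φ(1.96/√DE)]. At ICC 0 this returns 5.0%.

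| m | ICC | DE | 1.96/√DE | True level |
|---|---|---|---|---|
| 100 | 0.001 | 1.099 | 1.870 | 6.2% |
| 100 | 0.01 | 1.99 | 1.389 | 16.5% |
| 100 | 0.02 | 2.98 | 1.135 | 25.6% |
| 400 | 0.001 | 1.399 | 1.657 | 9.8% |
| 400 | 0.01 | 4.99 | 0.877 | 38.0% |
| 400 | 0.02 | 8.98 | 0.654 | 51.3% |

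**Step 2. Time to screening, simulated log-rank.** CHC rates were beta-distributed with no arm effect, and 35% were screened by day 180 (2,500 runs per cell). Balancing was imitated by taking, in each region, the best of the three 2+2 splits on baseline rate and then assigning arms at random. The columns vary the correlation between baseline rate and trial rate.

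| m / ICC | Correlation 0 (no credit) | 0.7 | 0.9 |
|---|---|---|---|
| 100 / 0.01 | 16% | 12% | 9% |
| 100 / 0.02 | 26% | 18% | 13% |
| 400 / 0.01 | 37% | 28% | 20% |
| 400 / 0.02 | 52% | 40% | 32% |

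The first column agrees with Step 1. A separate simulation at ICC 0, with 100 to 500 per CHC, gave 4.4% to 5.0%, so the inflation comes from clustering and not from the test itself.

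**Step 3. Colonoscopy, assuming 40% completion.** Entries are for 5 / 10 / 20 abnormal results per CHC, with no balancing.

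| ICC | Fisher, 180-day completion | Log-rank, time to colonoscopy |
|---|---|---|
| 0.01 | 2.6 / 3.9 / 5.1% | 5.6 / 6.6 / 7.0% |
| 0.05 | 3.8 / 7.0 / 12.7% | 7.5 / 10.7 / 16.4% |
| 0.10 | 5.8 / 12.1 / 21.8% | 10.4 / 16.0 / 26.0% |

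Fisher's test is conservative in small samples, which offsets part of the inflation. Completion of 30% or 50% moves each Fisher cell by at most 1 point. At ICC 0 the log-rank gives 4.6 / 5.1 / 5.7%.

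**Step 4. Stool-test results, Fisher, assuming 10% abnormal.** For ICC 0.005 / 0.01 / 0.02: 4.9 / 6.2 / 9.1% with 35 tests returned per CHC, and 11.3 / 17.9 / 29.1% with 140.

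**Step 5. Does a CHC-level analysis hold its level?** A linear model on the 8 CHC proportions with arm and region has 8 − 3 = 5 df. Without balancing it gave 4.1% to 5.4% for screening (m = 100 or 400, ICC 0 to 0.02) and 5.0% to 6.3% for colonoscopy (5 to 20 per CHC, ICC 0 to 0.10). With balancing it became conservative, at 0.6% to 3.4% for screening with ICC 0.01 to 0.02.

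**The case against.** The largest figures belong to time to screening, which is not a Protocol outcome and sits beside two screening proportions already analyzed with clustering. For colonoscopy completion, the one affected named outcome, five of the nine Fisher cells (2.6, 3.8, 3.9, 5.1 and 5.8%) are no higher than the top of the range for the CHC-level model. Clear inflation needs about 10 or more abnormal results per CHC and an ICC of about 0.05 or more. Both points stand. They limit the consequence, but the documents do not show that the trial falls in the harmless cells.

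The screening figures may also be high. Allocation was within region, so any regional share of the ICC cancels between arms, and balancing covered patient volume and race as well as baseline rate. If half the ICC is regional, the four settings fall to about 8/11/18/30% at correlation 0.7 and 6/10/13/18% at 0.9. That is smaller, but still above 5%.

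Three further points deserve weight:

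- The GEE models adjust for age and race/ethnicity and the log-rank test does not, so a disagreement between them could arise from that as well as from clustering.
- The arms use different assays, so equal result distributions are not an obvious null. Type I error is a weaker measure of harm there.
- The GEE itself has only 8 clusters and no stated small-sample correction. It recognizes clustering, which is all that is claimed for it here.

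**Conclusion.** The concern holds. The omission is plain in the text: the four comparisons are specified as tests for independent patients in a trial that randomized 8 CHCs. The magnitude is conditional, since CHC sizes, ICCs, event rates, the 4 v 4 split and the 5% level are all assumed.

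Time to screening is the most exposed if ICCs are of similar size across endpoints, because it has the most patients per CHC. A much larger ICC for colonoscopy would narrow that gap: by simulation, the time-to-colonoscopy log-rank at 10 per CHC and ICC 0.10 (16.0%) is about the same as time to screening at 100 per CHC and ICC 0.01 (16%). For colonoscopy completion the Fisher test may be close to 5% or well above it. This should be fixed, but it does not bear on the primary 90-day comparison.

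**What to change.** Amend the SAP's second paragraph and rerun the affected analyses.

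- **Time to screening.** Use a Cox model or score test clustered on CHC and stratified by region, with a named small-sample correction and a t reference distribution. It can carry the same age and race/ethnicity adjustment as the screening models. Ordinary robust variance is not dependable with 8 clusters, and this option was not simulated here, so its level should be checked at the actual CHC sizes. The alternative is to compare CHC-level Kaplan-Meier proportions at days 90 and 180; this largely repeats the existing screening endpoints.
- **Time to colonoscopy.** Do the same if counts allow.
- **Stool-test results and colonoscopy completion.** Compare CHC-level proportions in a model with arm and region, or use a GEE with an explicit small-sample correction. Where counts per CHC are too sparse, give counts and proportions without p-values. If the colonoscopy comparison is meant within each region, that is 2 v 2 CHCs and is best left descriptive.
- **Randomization test.** This cannot serve if regions were assigned separately. One chosen partition per region gives 2 × 2 = 4 allocations, so the smallest two-sided p is 2/4 = 0.50.
- **Interpretation.** State that the stool-test and colonoscopy comparisons are among patients selected after randomization, which cluster adjustment does not repair.
- **Reporting.** Give the CHC sizes and the estimated ICC for each endpoint.

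The cost is wording and reanalysis of data already held. P-values will be larger and intervals wider, and CHC-level tests will be conservative where balancing worked well (Step 5). The loss of power has not been quantified.

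### Time to screening, test results and colonoscopy are compared with unadjusted tests, so they may be confounded by the age and race/ethnicity imbalance the SAP reports, and they ignore CHC clustering

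*SAP*

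**What the plan says.** Everything on this point is in the SAP, mainly its second paragraph. Screening within 90 or 180 days is analyzed by "logistic regression models with the generalized estimating equations to account for the correlated nature of data within CHCs", with a stated adjustment: "adjusting for age and race/ethnicity, which were unbalanced between the two arms".

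Four further arm comparisons are given without covariates, strata for age or race/ethnicity, or a cluster term:

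- Time to screening: "We compared time to screening participation between the two arms using a log-rank test".
- Stool test results, among those who returned a test: "we compared the distribution of test results between study arms using Fisher's exact tests".
- Colonoscopy, among those with an abnormal result: "we compared the rate of colonoscopy completion within 180 days by arm and region using Fisher's exact tests".
- Time to colonoscopy, in the same subset: "compared time to colonoscopy completion between the two arms using a log-rank test".

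The SAP's first paragraph adds one other way of handling imbalance: "A secondary analysis used a propensity score matched sample to ensure balance between the two groups on age, gender, race/ethnicity and insurance status". It does not say which outcomes that analysis covers.

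The protocol's Objective section lists colonoscopy completion within 180 days of an abnormal result as a secondary outcome. Time to screening, time to colonoscopy and the distribution of test results are not listed there as outcomes.

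**The concern.** The SAP treats the imbalance as serious enough to adjust the primary model, then leaves it unaddressed in the next comparison of the same patients. Time to screening is built from the same screening events as the 180-day proportion. A reader will set the two results side by side, yet one is adjusted and cluster-aware and the other is neither.

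Two distinct problems follow. If age or race/ethnicity predicts screening, the imbalance shifts the unadjusted contrast itself. Separately, log-rank and Fisher tests treat patients as independent although whole CHCs were allocated, so their p-values can be too small even when the contrast is unbiased.

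Imbalance is unsurprising in this design. Under Methods, the protocol allocates only 8 CHCs, choosing groupings that were close on patient volume, racial distribution and baseline screening rate. Age was not among the balancing factors, and the SAP reports that race/ethnicity was unbalanced all the same.

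**Working it through.** **No figure to reproduce.** The documents give no sample size, outcome rate, ICC or measure of imbalance. All inputs below are assumptions, chosen to show a range. There is no true arm effect in any of them.

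**Step 1: bias from imbalance.** Take one binary covariate. The false difference between arms is the imbalance in its share times the difference in screening rate between its levels. Imbalances of 10 to 30 points and prognostic differences of 5 to 10 points give 0.10 × 5 = 0.5 points up to 0.30 × 10 = 3.0 points. If the prognostic difference is 0, so is the bias.

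**Step 2: effect on a two-sided 5% test, independent patients.** Take rates of 25% and 35% by covariate level and shares of 60% and 40%. The arm rates are then 0.25 + 0.10 × 0.60 = 0.31 and 0.25 + 0.10 × 0.40 = 0.29. With 1,000 per arm, SE = √(2 × 0.30 × 0.70 / 1,000) = 0.0205, so the shift is 0.02 / 0.0205 = 0.98 SE. Rejection = 1 − Φ(1.96 − 0.98) + Φ(−1.96 − 0.98) = 16.4%. Over the whole range in step 1, rejection runs from 5.4% to 17.9% at 500 per arm and from 6.8% to 63.9% at 2,500 per arm.

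**Step 3: the log-rank test itself.** Simulation used 400 trials per setting, 1,000 per arm, exponential times grouped in weeks to week 26, and no clustering.

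| Imbalance | 180-day rates by covariate level | Unadjusted log-rank | Stratified on the covariate |
|---|---|---|---|
| 10 points | 25% vs 35% | 8.0% | 3.8% |
| 20 points | 25% vs 35% | 16.5% | 3.8% |
| 30 points | 25% vs 35% | 25.5% | 5.3% |
| 20 points | 25% vs 30% | 8.3% | 4.5% |

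The Monte Carlo SE near 5% is √(0.05 × 0.95 / 400) = 1.1 points, so the stratified column agrees with the nominal level. Using the covariate corrects the bias due to that covariate.

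**Step 4: colonoscopy subset.** Assume 25 to 100 patients per arm with an abnormal result, a rate of 45% at the lower covariate level, prognostic differences of 10 or 20 points and imbalances of 10 to 30 points. The false difference is 1 to 6 points and rejection is 5.1% to 13.7%. The covariate effect on the test is modest here because the subset is small.

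**Step 5: clustering alone.** The design effect is DE = 1 + (m − 1) × ICC, with m patients per CHC. A nominal 5% individual-level test then rejects with probability 2 × [1 − Φ(1.96 / √DE)]. For m = 125 and ICC = 0.01, DE = 1 + 124 × 0.01 = 2.24 and rejection is 19.0%.

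| Assumed ICC | m = 125 | m = 250 |
|---|---|---|
| 0.001 | 6.4% | 7.9% |
| 0.01 | 19.0% | 29.4% |
| 0.05 | 46.5% | 59.3% |

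With four CHCs per arm, 1,000 patients per arm corresponds to m = 250. For the colonoscopy subset, with 6 to 25 per CHC and ICC 0.01 to 0.05, rejection is 5.6% to 18.6%. For time to screening, clustering can therefore matter at least as much as the imbalance.

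Steps 2 to 4 and step 5 are not additive. Differences in case mix between CHCs are themselves part of the between-CHC variance.

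**The case against.** A reader might infer that these contrasts are confounded as a matter of fact, and that the primary model removes the confounding. The documents support neither. They give no size or direction for the imbalance and no link between age or race/ethnicity and these outcomes. They report the imbalance for the arms, not for the patients who returned a test or had an abnormal result. The GEE model adjusts for two measured covariates across 8 CHCs, whereas the SAP's own matching set also includes gender and insurance.

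The propensity-matched analysis might already cover these outcomes. That is possible, but its scope is not stated, and it is a secondary analysis. The tests named in the SAP remain unadjusted.

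The rejection rates in steps 2 to 4 are conditional on a fixed imbalance among independent patients. With 1,000 individually randomized patients per arm, the SE of a difference in a 50% share is √(2 × 0.25 / 1,000) = 2.2 points, so a 10-point gap would be about 4.5 SE. Such gaps become plausible because whole CHCs were allocated. This stands: the rates are illustrations, not the trial's type I error. It also means that covariate adjustment without a cluster term would be only half a remedy.

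A disagreement between the log-rank test and the 180-day model could not be put down to the imbalance alone. The two also differ in their treatment of clustering and in target: a whole time course against a proportion at a fixed time.

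The test-result comparison contrasts two different assays among people selected after randomization by returning a kit. Baseline adjustment would not make that a randomized comparison. The colonoscopy subset has the same limitation.

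Finally, the SAP describes most analyses in the past tense, so any models added now may be post hoc. That affects how they are labeled, not whether they are worth having.

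**Conclusion.** The point holds as a gap in consistency and a risk of bias, not as demonstrated confounding. The SAP acknowledges an imbalance, adjusts for it in one set of models, and names unadjusted tests that also ignore CHC clustering for four other comparisons.

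The case is strongest for time to screening, which uses all randomized patients and shares its events with the 180-day model. On assumed inputs, the imbalance raises the log-rank rejection rate from 5% to between 8% and 26% at 1,000 per arm, and clustering at an ICC of 0.01 raises it to 19% to 29% at 125 to 250 per CHC. It is weaker for colonoscopy, where the assumed covariate effect is modest, but completion within 180 days is a listed secondary outcome and should not rest on an unadjusted Fisher test alone. It is weakest for test results, where the right response is a label rather than a model.

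The 90- and 180-day screening analyses are not affected by this point.

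**What to change.** 1. **Time to screening.** Replace the log-rank test with a Cox or discrete-time model for arm, adjusted for age and race/ethnicity as in the primary model. Use cluster-robust variance or a frailty term by CHC, with a small-cluster correction because there are only 8 CHCs. Unadjusted curves can stay as description.
2. **Colonoscopy within 180 days and time to colonoscopy.** Add a model for each, adjusted for age and collapsed race/ethnicity, penalised if cells are sparse, and accounting for CHC where counts allow. If counts do not allow it, label the Fisher and log-rank tests descriptive.
3. **Test results.** Keep the comparison, but label it descriptive and say that it contrasts two assays among people who returned a kit.
4. **Propensity-matched analysis.** State which outcomes it covers.
5. **Labeling.** Where results were already known when a model was added, report that model as post hoc.

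The cost is a few lines of SAP text and SAS code, using covariates already in the data set. The main downside is some instability in the colonoscopy models if abnormal results are few, which is why item 2 has a fallback.

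### FIT brand coincides with region, yet test results are compared in one unstratified table by arm; a region-stratified comparison is a cheap, low-priority improvement

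*SAP*

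**What the plan says.** The Protocol's Methods (FIT arm paragraph) state that in each CHC "we used the FIT kit brand already in routine use (Boston: Polymedco; LA and SD: Hemosure iFOB test"). The same section says "Randomization was limited to the 8 CHCs in Boston and LA", and describes the allocation: "Within each region, we considered the permutations of assigning the four CHCs into two arms". The chosen split was the one closest on patient volume, racial distribution and baseline screening rate. The FIT-DNA arm was mailed a single manufacturer's kit, returned to that manufacturer's laboratory.

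The second paragraph of the SAP defines the analysis set for test results as "Among participants who returned stool tests within 180 days". The analysis is that "we compared the distribution of test results between study arms using Fisher's exact tests". No region or brand stratum is given. The next sentence, on follow-up colonoscopy, does name region: "we compared the rate of colonoscopy completion within 180 days by arm and region using Fisher's exact tests". Region also appears earlier in that paragraph among the "subgroup analyses for pre-specified subgroups of interest (region, race/ethnicity, age, and language"), but that list follows the screening-participation analyses and is not tied to test results.

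**The concern.** Within the randomized FIT arm, brand and region are the same variable. A FIT abnormal rate pooled over Boston and LA is therefore a weighted mean over two products and two populations, with weights set by how many kits each region returned. The allocation balanced CHC groups on patient volume, among other things. The analysis set, however, is the people who returned a stool test, which is determined after randomization, so nothing fixes the regional mix of returns or makes it equal between arms.

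The abnormal rate shows how many people each strategy sends on to colonoscopy. An unstratified table also leaves out region, within which allocation was made. A reader could take the pooled FIT figure as a property of one test, or read a regional difference as a population difference when it could equally come from the brand.

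**Working it through.** The documents give no abnormal rates, no positivity thresholds and no returned-kit counts by region. There is no figure of the plan's to reproduce, and every rate, share and count below is an assumption.

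**Notation.** Let w and v be the Boston share of returned kits in the FIT and FIT-DNA arms. Let pB and pL be the FIT-arm abnormal rates in Boston and LA, and qB and qL those in the FIT-DNA arm.

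- Pooled FIT rate: F = w·pB + (1 − w)·pL
- Pooled FIT-DNA rate: D = v·qB + (1 − v)·qL
- Rearranged: D − F = [v(qB − pB) + (1 − v)(qL − pL)] + (v − w)(pB − pL)

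The bracket is a weighted average of the two within-region differences. The last term is confounding by region. It is zero if the mix is the same in both arms (v = w) or if the FIT rates are equal (pB = pL).

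**Step 1: equal FIT rates.** With pB = pL = 6%, F = 6.0% at every mix. There is no dependence and no confounding.

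**Step 2: rates differ, FIT-DNA rate the same in both regions.** Because qB = qL, D does not depend on mix. Take FIT at 5% with one brand and 10% with the other, and FIT-DNA at 12%.

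- Within-region odds ratios: (0.12/0.88)/(0.05/0.95) = 2.59 and (0.12/0.88)/(0.10/0.90) = 1.23.

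| Share of FIT returns from lower-rate brand | Pooled FIT rate | Pooled odds ratio |
|---|---|---|
| 30% | 8.5% | 1.47 |
| 50% | 7.5% | 1.68 |
| 70% | 6.5% | 1.96 |

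Every pooled value lies between 1.23 and 2.59. Where the arms share a common mix, this is averaging of unequal regional effects and not bias.

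**Step 3: effect on the test.** Assume 500 returned kits per arm, FIT-DNA at 10% in both regions, and FIT at 4% in Boston and 8% in LA.

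- Boston share 20%: F = 0.2 × 4% + 0.8 × 8% = 7.2%, difference 2.8 points, Fisher p = 0.14.
- Boston share 80%: F = 0.8 × 4% + 0.2 × 8% = 4.8%, difference 5.2 points, Fisher p = 0.002.

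The two results differ only in the regional mix of FIT returns.

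**Step 4: mix differs between arms, no arm difference in either region.** Assume both arms have 4% in Boston and 10% in LA, with w = 35% and v = 65%.

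- F = 0.35 × 4% + 0.65 × 10% = 7.9%
- D = 0.65 × 4% + 0.35 × 10% = 6.1%
- D − F = −1.8 points, all of it from the last term: (0.65 − 0.35) × (4% − 10%) = −1.8 points.

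This is confounding proper. It shrinks with the imbalance: a 5-point gap in mix at the same rates gives 0.05 × 6 = 0.3 points. A region-stratified analysis would return no difference in either case, because both within-region odds ratios are 1.

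**The case against.** The distribution of test results is not a named outcome. The Protocol's Objective lists 90-day completion as primary, with 180-day completion and follow-up colonoscopy as secondary. The trial is described as pragmatic and compares outreach approaches, not assays, and each CHC used its customary FIT. A pooled rate for FIT as routinely used is therefore a coherent arm-level quantity. Allocation within region, with matching on patient volume and baseline screening rate, also limits any imbalance in regional mix. All of this stands, and it is why the point is minor. What remains is that differential return can still unbalance the mix, and the SAP neither stratifies nor declares the pooled quantity as its target.

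Three stronger readings are tempting, and the documents support none of them.

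- *The two brands have different abnormal rates, so the pooled result is biased.* No rates or thresholds are given. The size and direction of any effect are unknown and may be zero.
- *FITs done in clinic by FIT-DNA-arm patients contaminate that arm's results.* The phrase "using any screening modality (FIT, FIT-DNA, colonoscopy") belongs to the completion outcome. The SAP does not say whether stool tests other than the mailed kit count in the test-result comparison. If they do, tabulating by arm still preserves the randomized groups.
- *Stratifying would show whether brand or population drives a regional difference.* It cannot, because the two are fully aligned.

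**Conclusion.** The point holds in conditional form. Brand coincides with region in the randomized FIT arm, and the test-result comparison is one unstratified Fisher's exact test by arm. If FIT abnormal rates differ by region or brand, the pooled FIT rate moves with the regional mix of returned kits. The arm contrast is confounded by (v − w)(pB − pL) if the mix also differs between arms. In the assumed cases this ranges from nothing (equal rates or equal mix) to 1.8 points (35% against 65% Boston share, rates of 4% and 10%). The documents do not show whether either condition occurs.

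A reader might infer an analysis error or a threat to the trial's main conclusion. Neither follows: the pooled rate is a legitimate description of the strategies as delivered, and the 90-day completion endpoint is untouched. This is a cheap improvement of low priority to a supporting comparison.

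**What to change.** In the SAP sentence on test results:

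1. Report the number and proportion abnormal by arm within region, which in the FIT arm is the same as by brand.
2. Make the arm comparison region-stratified, for example by Mantel-Haenszel or an exact conditional method, with a check that the two regional odds ratios agree.
3. Keep the pooled arm-level rate, labelled as a description of FIT as routinely used.
4. State that a regional difference in FIT abnormal rate cannot be separated from brand.
5. State whether stool tests other than the mailed kit are included. A table by test performed may be added as a supplement, not as a replacement for the comparison by arm.

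The cost is SAP wording and one table; the SAP already uses region elsewhere. Cells will be smaller and each regional estimate less precise. Only four CHCs per region are shared between the two arms, so each regional contrast rests on very few clinics. Stratifying by region also does not address clustering within CHCs, so the regional results should be read as descriptive.
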